10.1.12 Outcome

- Recovered/Resolved – Subject returned to first assessment status with respect to the AE/PTE.
- Recovering/Resolving – the intensity is lowered by one or more stages: the diagnosis or signs/symptoms has almost disappeared; the abnormal laboratory value improved, but has not returned to the normal range or to baseline; the subject died from a cause other than the particular AE/PTE with the condition remaining “recovering/resolving”.
- Not recovered/not resolved – there is no change in the diagnosis, signs or symptoms; the intensity of the diagnosis, signs/ symptoms or laboratory value on the last day of the observed study period has got worse than when it started; is an irreversible congenital anomaly; the subject died from another cause with the particular AE/PTE state remaining “Not recovered/not resolved”.
- Resolved with sequelae – the subject recovered from an acute AE/PTE but was left with permanent/significant impairment (eg, recovered from a cardiovascular accident but with some persisting paresis).
- Fatal – the AEs/PTEs which are considered as the cause of death.
- Unknown – the course of the AE/PTE cannot be followed up due to hospital change or residence change at the end of the subject’s participation in the study.

10.2 Procedures

10.2.1 Collection and Reporting of AEs

10.2.1.1 PTE and AE Collection Period

Collection of PTEs will commence from the time the subject signs the informed consent to participate in the study and continue until the subject is first administered study medication (Visit 1) or until screen failure. For subjects who discontinue prior to study medication administration, PTEs are collected until the subject discontinues study participation.

Collection of AEs will commence from the time that the subject is first administered study medication (Visit 1). Routine collection of AEs will continue 3 weeks after the last dose of study drug.

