9.3.2 Randomization

Randomization will take place on Day1 (could be the same day at which Screening visit took place). The following procedures will be performed and documented during Randomization:

- Vital Signs (if not same day as Screening procedures).
- Concomitant medications.
- Adverse Events.
- The following parameters will be assessed by the investigator: presence of muscle spasm, presence of local pain, limitation of activities of daily living, and limitation of range of motion.
- Subject Diary dispense. Subjects should be instructed :
 - To complete assessment for Day 1 at the hospital before the first drug intake.
 - Starting from Day 2 record the following assessments (compared to Baseline) in the daily diary: rating of medication helpfulness, relief from local pain, subject-rated Clinical global impression, restriction in activities of daily living, and restriction of movement;
 - To record the following assessments in the daily diary: **Company Confidential Information** intensity of local pain **Company Confidential Information** ;
 - To complete their diary during 14 days at the same time each day if possible but record the worst feeling/symptom since the diary was last completed. No diary to be completed at Day 15 (Visit 4) but returned to the Investigator.
 - To bring their diary to each study visit for review by Investigator. Completed pages will be collected by Investigator, then the diary will be dispensed to subject again.
- If the subject has satisfied all of the inclusion criteria and none of the exclusion criteria for randomization, the subject should be randomized using the IVRS/IWRS, as described in Section 8.2.
- Study drug dispense. The medication identification (ID) number of the study drug will be provided via IVRS/IWRS. To avoid any overdose and non-compliance with study drug intake, original bottle containing 60 capsules with CER 15 mg or Placebo will be opened in front of the subject and 40 capsules of 60 will be removed in cleanliness condition and put into the additional bottle for keeping at the site (never dispensed to subject) until destruction. Original bottle containing 20 capsules with CER 15 mg or Placebo will be dispensed to subject. Subject will be instructed to:
 - To swallow one capsule whole with 180 mL of room temperature water, once daily in the evening between 18:00 and 19:00 starting from Day1.

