10.0 PRETREATMENT EVENTS AND ADVERSE EVENTS

10.1 Definitions

10.1.1 PTEs

A PTE is defined as any untoward medical occurrence in a clinical investigation subject who has signed informed consent to participate in a study but prior to administration of any study medication; it does not necessarily have to have a causal relationship with study participation.

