- Pre-existing conditions (present at the time of signing of informed consent) are considered concurrent medical conditions and should NOT be recorded as PTEs or AEs. Baseline evaluations (eg, laboratory tests, ECG, X-rays etc.) should NOT be recorded as PTEs unless related to study procedures. However, if the subject experiences a worsening or complication of such a concurrent condition, the worsening or complication should be recorded appropriately as a PTE (worsening or complication occurs before start of study medication) or an AE (worsening or complication occurs after start of study medication). Investigators should ensure that the event term recorded captures the change in the condition (eg, “worsening of...”).
- If a subject has a pre-existing episodic condition (eg, asthma, epilepsy) any occurrence of an episode should only be captured as a PTE/AE if the episodes become more frequent, serious or severe in nature, that is, investigators should ensure that the AE term recorded captures the change in the condition from Baseline (eg “worsening of...”).
- If a subject has a degenerative concurrent condition (eg, cataracts, rheumatoid arthritis), worsening of the condition should only be captured as a PTE/AE if occurring to a greater extent to that which would be expected. Again, investigators should ensure that the AE term recorded captures the change in the condition (eg, “worsening of...”).

Worsening of PTEs or AEs:

- If the subject experiences a worsening or complication of a PTE after starting administration of the study medication, the worsening or complication should be recorded appropriately as an AE. Investigators should ensure that the AE term recorded captures the change in the condition (eg, “worsening of...”).
- If the subject experiences a worsening or complication of an AE after any change in study medication, the worsening or complication should be recorded as a new AE. Investigators should ensure that the AE term recorded captures the change in the condition (eg, “worsening of...”).

Changes in severity of AEs /Serious PTEs:

- If the subject experiences changes in severity of an AE/serious PTE, the event should be captured once with the maximum severity recorded.

Preplanned surgeries or procedures:

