10.1.8 Start Date

The start date of the AE/PTE is the date that the first signs/symptoms were noted by the subject and/or physician.

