13.1.4.1 AEs

All AEs will be coded by system organ class, high level term, and preferred term using MedDRA. TEAEs are defined as AEs with onset occurring within 30 days (onset date – last date of dose +1≤30) after study drug administration. TEAEs will be summarized by treatment group and dosing frequency by system organ class and preferred term. The following summary tables will be included in the report: summary of TEAEs and drug-related TEAEs, relationship of TEAEs to study drug (related vs. not-related), severity of TEAEs and related TEAEs. Data listings will be provided for all AEs including PTE, TEAEs, AEs leading to study drug discontinuation, and SAEs.

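### The Randomization visit lists adverse events although no drug has yet been taken, and because onset is recorded by date only, a misclassified Day 1 event cannot be corrected at analysis

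*Protocol*

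**What the plan says.** - **Definition.** Section 10.1.1 defines a PTE as an event in a subject who has "signed informed consent to participate in a study but prior to administration of any study medication". Section 10.1.3 applies the same rule to pre-existing conditions: worsening is an AE when the "worsening or complication occurs after start of study medication".
- **Collection periods.** Under 10.2.1.1, PTE collection will "continue until the subject is first administered study medication (Visit 1) or until screen failure". For AEs it says "Collection of AEs will commence from the time that the subject is first administered study medication (Visit 1", closing the bracket there. Both sentences attach the Visit 1 label to the first dose.
- **Visit lists.** Section 9.3.1 lists PTEs at Screening. Section 9.3.2 lists AEs, and no PTEs, at Randomization on Day 1.
- **First dose.** Section 9.3.2 dispenses the bottle at Randomization, has the Day 1 diary assessment done at the site ahead of the first intake, and schedules the capsule "once daily in the evening between 18:00 and 19:00 starting from Day1".
- **Timing recorded.** Section 10.1.8: "The start date of the AE/PTE is the date that the first signs/symptoms were noted by the subject and/or physician". The event items in 10.2.1.2 include start and stop dates and no clock time.
- **Analysis rule.** Section 13.1.4.1: "TEAEs are defined as AEs with onset occurring within 30 days". The sentence goes on to require that this be after dosing, and gives a date inequality counted from the last dose.

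**The concern.** The visit list in 9.3.2 and the label in 10.2.1.1 point a site towards recording, as AEs, events that the protocol's own definition makes PTEs. The neutral question suggested in 10.2.1.2 asks about the time since the previous visit, so at Randomization it covers a period wholly before drug.

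The class matters in the record. Section 10.2.1.2 asks for drug causality and action on study drug for AEs and not for PTEs. It requires every AE to be followed, but no follow-up of non-serious PTEs. A pre-dose event entered as an AE would be judged for a causal link that cannot exist, and could then be counted as treatment-emergent. Section 9.3.2 allows Screening and Randomization on the same day, so procedure-related events such as a bruise after a blood draw can fall in these hours.

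**Working it through.** The protocol gives no figure of its own on this point, so none is reproduced.

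**Step 1. Order on Day 1.** By 9.3.2 the sequence is the visit and its event inquiry, dispensing, then the evening capsule. Section 10.1.1 classes everything before that capsule as a PTE. The 9.3.2 list calls it an AE, and 10.2.1.1 ties the first dose to the visit. These statements do not agree.

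**Step 2. What the dates can separate.**

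| Onset | Compared with first-dose date | Separable by date? |
|---|---|---|
| Between consent and the day before Day 1 | earlier | yes |
| Day 1 | equal | no |
| Day 2 onward | later | yes |

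Only Day 1 onsets depend entirely on the class the investigator entered.

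**Step 3. The inequality in 13.1.4.1.** It is onset date − last-dose date + 1 ≤ 30. With the last dose on Day 14:
- Onset on Day 1: 1 − 14 + 1 = −12, which passes.
- Onset five days before Day 1 (Day −4, counting the day before Day 1 as Day 0): −4 − 14 + 1 = −17, which also passes.

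The formula has no lower limit. Only the accompanying words exclude pre-dose onsets, and for Day 1 the dates cannot apply those words.

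**Step 4. Size.** Inputs are N = 180 subjects (sections 2.0 and 6.1), dosing between 18:00 and 19:00 (9.3.2), and an assumed background rate of 0.01 events per subject-day, which is not in the protocol. Expected events = N × (hours before dose / 24) × rate.
- All of Day 1 before 18:00: 180 × 18/24 × 0.01 = 1.35
- All of Day 1 before 19:00: 180 × 19/24 × 0.01 = 1.43
- Eight hours before the dose (assumed, since visit times are not given): 180 × 8/24 × 0.01 = 0.6

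The ceiling is about 1.4 events, or about 0.7 in each arm of 90. It scales with the assumed rate: half the rate gives about 0.7 in total and twice the rate about 2.9. It also supposes that every such event is misclassified.

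**Step 5. Effect on the comparison.** Pre-dose events are equally likely in both randomized arms. Adding the same expected number to each leaves the expected difference in event counts unchanged and pulls the ratio towards 1. For the proportion of subjects with an event, if pre-dose events are independent of later ones, the difference is multiplied by 1 − b. Here b = 1.43/180 = 0.008, so it shrinks by less than 1%.

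**The case against.** The strongest reply is that the governing rule is already right. Sections 10.1.1, 10.1.3 and 10.2.1.1 all turn on administration of drug, and the visit number is only a label. The wording in 13.1.4.1 requires onset after dosing. Investigators classify each event on a shared PTE/AE page, two fields do not apply to PTEs, and PTEs appear in the listings. All of this stands. A reader might infer that the protocol places the boundary at Visit 1, or that pre-dose events can never be separated afterwards. Neither follows: an event classified by the definition stays separable.

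A reader might also count the Screening interval of up to five days as exposed. It is not, because those onsets carry an earlier date than the first dose and can be identified by date. Nor does same-day Screening bring withdrawal of the listed analgesics into the pre-dose hours: sections 7.2 and 7.3 require 3 or 14 days without them. Procedure-related events have their own causality item (10.1.7, 10.2.1.2), which softens that part of the concern.

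It can also be said that same-day onset rules belong in the SAP or CRF, neither of which is at hand. That holds for the analysis rule. It does not hold for the data: no SAP can recover an order of events that was not captured, and the protocol's list of items to record does not capture it. The upper part of the Appendix A schedule is also missing from the text reviewed, so its label for event collection at Visit 1 could not be checked.

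**Conclusion.** The point holds in a narrow form. The Randomization list in 9.3.2 and the label in 10.2.1.1 conflict with the evening first dose and with the PTE definition. A Day 1 event misclassified as a result cannot be corrected from dates. The effect is small: at most about 1.4 events across both arms at the assumed rate of 1 per 100 subject-days, with slight dilution of ratios and almost no change in the expected risk difference. Section 13.1.4.1 plans summaries of adverse events and names no between-arm test, so no formal safety conclusion is at risk. The case for acting is that a visit instruction contradicts the protocol's own definition and that the correction is nearly free.

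**What to change.** 1. In 9.3.2, list Pre-Treatment Events in place of Adverse Events at Randomization, and align Appendix A if it differs.
2. In 10.2.1.1, delete the Visit 1 label in both sentences or replace it with a reference to the first dose.
3. In 10.2.1.2 and the CRF, add a before/after-first-dose indicator for events that start on Day 1.
4. In 13.1.4.1, state that a treatment-emergent event has onset at or after the first dose, using the indicator for Day 1 onsets.

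The cost is a few lines of protocol wording and one extra CRF field, completed only for Day 1 events. No dose, schedule or clinical rule changes.

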10.2.1.2 PTE and AE Reporting

At each study visit, the investigator will assess whether any subjective AEs have occurred. A neutral question, such as “How have you been feeling since your last visit?” may be asked. Subjects may report AEs occurring at any other time during the study. Subjects experiencing a serious PTE must be monitored until the symptoms subside and any clinically relevant changes in laboratory values have returned to baseline or there is a satisfactory explanation for the change. Non-serious PTEs, related or unrelated to the study procedure, need not to be followed-up for the purposes of the protocol.

All subjects experiencing AEs, whether considered associated with the use of the study medication or not, must be monitored until the symptoms subside and any clinically relevant changes in laboratory values have returned to baseline or until there is a satisfactory explanation for the changes observed. All PTEs and AEs will be documented in the PTE/AE page of the (e)CRF, whether or not the investigator concludes that the event is related to the drug treatment. The following information will be documented for each event:

1. Event term.
2. Start and stop date.
3. Severity.
4. Investigator’s opinion of the causal relationship between the event and administration of study medication(s) (related or not related) (not completed for PTEs).
5. Investigator’s opinion of the causal relationship to study procedure(s), including the details of the suspected procedure.
6. Action concerning study medication (not applicable for PTEs).
7. Outcome of event.
8. Seriousness.

Patient diaries will not be used as a primary means to collect AEs. However, should the investigator become aware of a potential AE through the information collected with this instrument, proper follow-up with the patient for medical evaluation should be undertaken. Through this follow-up if it is determined that an AE not previously reported has been identified, normal reporting requirements should be applied.

10.2.2 Collection and Reporting of SAEs

When an SAE occurs through the AE collection period it should be reported according to the following procedure:

A Takeda SAE form must be completed, in English, and signed by the investigator immediately or within 24 hours of first onset or notification of the event. The information should be completed as fully as possible but contain, at a minimum:

- A short description of the event and the reason why the event is categorized as serious.
- Subject identification number.
- Investigator’s name.
- Name of the study medication(s)

CONFIDENTIAL

- Causality assessment.

The SAE form should be transmitted within 24 hours to the attention of the contact listed in Section 1.1.

Any SAE spontaneously reported to the investigator following the AE collection period should be reported to the sponsor if considered related to study participation.

Reporting of Serious PTEs will follow the procedure described for SAEs.

10.2.3 Reporting of Abnormal Liver Function Tests

If a subject is noted to have ALT or AST elevated $>3 \times \text{ULN}$ on 2 consecutive occasions, the abnormality should be recorded as an AE. If a subject is noted to have ALT or AST $>3 \times \text{ULN}$ and total bilirubin $>2 \times \text{ULN}$ for which an alternative etiology has not been identified, the event should be recorded as an SAE and reported as per Section ~~10.2.2~~10.2.2. The investigator must contact the Medical Monitor for discussion of the relevant subject details and possible alternative etiologies, such as acute viral hepatitis A or B or other acute liver disease or medical history/concurrent medical conditions. Follow-up laboratory tests as described in Section 9.1.9 must also be performed.

10.3 Follow-up of SAEs

If information not available at the time of the first report becomes available at a later date, the investigator should complete a follow-up SAE form or provide other written documentation and fax it immediately, within 24 hours of receipt. Copies of any relevant data from the hospital notes (eg, ECGs, laboratory tests, discharge summary, postmortem results) should be sent to the addressee, if requested.

All SAEs should be followed up until resolution or permanent outcome of the event. The timelines and procedure for follow-up reports are the same as those for the initial report.

10.3.1 Safety Reporting to Investigators, IRBs or IECs, and Regulatory Authorities

The sponsor will be responsible for reporting all suspected unexpected serious adverse reactions (SUSARs) and any other applicable SAEs to regulatory authorities, investigators and IRBs or IECs, as applicable, in accordance with national regulations in the countries where the study is conducted. Relative to the first awareness of the event by/or further provision to the sponsor or sponsor's designee, SUSARs will be submitted to the regulatory authorities as expedited report within 7 days for fatal and life-threatening events and 15 days for other serious events, unless otherwise required by national regulations. The sponsor will also prepare an expedited report for other safety issues where these might materially alter the current benefit-risk assessment of an investigational medicinal product or that would be sufficient to consider changes in the investigational medicinal products administration or in the overall conduct of the trial. The investigational site also will forward a copy of all expedited reports to his or her IRB or IEC in accordance with national regulations.

11.0 STUDY-SPECIFIC COMMITTEES

No steering committee, data safety monitoring committee, or clinical endpoint committee will be used in this study.

12.0 DATA HANDLING AND RECORDKEEPING

The full details of procedures for data handling will be documented in the Data Management Plan. AEs, PTEs, medical history, and concurrent conditions will be coded using the Medical Dictionary for Regulatory Activities (MedDRA). Drugs will be coded using the World Health Organization (WHO) Drug Dictionary.

12.1 CRFs

Completed (e)CRFs are required for each subject who signs an informed consent.

The sponsor or its designee will supply investigative sites with access to eCRFs. The sponsor will make arrangements to train appropriate site staff in the use of the eCRF. These forms are used to transmit the information collected in the performance of this study to the sponsor and regulatory authorities. (e)CRFs must be completed in English.

After completion of the entry process, computer logic checks will be run to identify items, such as inconsistent dates, missing data, and questionable values. Queries may be issued by Takeda personnel (or designees) and will be answered by the site.

Corrections are recorded in an audit trail that captures the old information, the new information, identification of the person making the correction, the date the correction was made, and the reason for change. Reasons for significant corrections should additionally be included.

The principal investigator must review the (e)CRFs for completeness and accuracy and must sign and date the appropriate (e)CRFs as indicated. Furthermore, the investigator must retain full responsibility for the accuracy and authenticity of all data entered on the (e)CRFs.

(e)CRFs will be reviewed for completeness and acceptability at the study site during periodic visits by study monitors. The sponsor or its designee will be permitted to review the subject's medical and hospital records pertinent to the study to ensure accuracy of the (e)CRFs. The completed (e)CRFs are the sole property of the sponsor and should not be made available in any form to third parties, except for authorized representatives of appropriate governmental health or regulatory authorities, without written permission of the sponsor.

12.2 Record Retention

The investigator agrees to keep the records stipulated in Section 12.1 and those documents that include (but are not limited to) the study-specific documents, the identification log of all participating subjects, medical records, temporary media such as thermal sensitive paper, source worksheets, all original signed and dated informed consent forms, subject authorization forms regarding the use of personal health information (if separate from the informed consent forms), {copies of all paper CRFs and query responses/ electronic copy of eCRFs, including the audit trail}, and detailed records of drug disposition to enable evaluations or audits from regulatory authorities, the sponsor or its designees. Any source documentation printed on degradable thermal sensitive paper should be photocopied by the site and filed with the original in the subject's chart to ensure long term legibility. Furthermore, International Conference on Harmonisation (ICH) E6 Section 4.9.5 requires the investigator to retain essential documents specified in ICH E6 (Section 8) until at least 2 years after the last approval of a marketing application for a specified drug indication being investigated or, if an application is not

approved, until at least 2 years after the investigation is discontinued and regulatory authorities are notified. In addition, ICH E6 Section 4.9.5 states that the study records should be retained until an amount of time specified by applicable regulatory requirements or for a time specified in the Clinical Study Site Agreement between the investigator and sponsor.

Refer to the Clinical Study Site Agreement for the sponsor's requirements on record retention. The investigator should contact and receive written approval from the sponsor before disposing of any such documents.

